#### **6.2.2.4. Time to response**

Time to response (TTR) is defined, for patients with OR, as the time from the 'start date' to the first documentation of objective response (CR or PR) which is subsequently confirmed.

$$\text{TTR (in months)} = [\text{first date of OR} - \text{'start date'} + 1] / 30.4375$$

TTR will be summarized using simple descriptive statistics (mean, SD, median, min, max, Q1, Q3).

#### **6.2.2.5. Progression-free survival**

Progression-Free Survival (PFS) is defined as the time from the ‘start date’ to the date of the first documentation of PD or death due to any cause, whichever occurs first.

PFS data will be censored on the date of the last adequate tumor assessment for patients who do not have an event (PD or death), for patients who start a new anti-cancer therapy prior to an event (see Section 5.2.6) or for patients with an event after 2 or more missing tumor assessments. Patients who do not have an adequate baseline tumor assessment or who do not have an adequate post-baseline tumor assessment will be censored on the ‘start date’ unless death occurred on or before the time of the second planned tumor assessment (ie,  $\leq 12$  weeks after the ‘start date’) in which case the death will be considered an event.

In this study antitumor activity will be assessed through radiological tumor assessments conducted at screening and every 6 weeks until PD regardless of initiation of subsequent anti-cancer therapy. After 1 year from the ‘start date’, tumor assessments will be conducted less frequently, ie, at 12-week intervals.

The censoring and event date options to be considered for the PFS and DR analysis are presented in Table 4.

$$\text{PFS (months)} = [\text{date of event or censoring} - \text{‘start date’} + 1] / 30.4375$$

**Table 4. Outcome and event dates for PFS and DR analyses**

Scenario	Date of event/censoring	Outcome
No adequate baseline assessment	‘Start date’	Censored a
PD or death - After at most one missing or inadequate post-baseline tumor assessment, OR - $\leq 12$ weeks after the ‘start date’	Date of PD or death	Event
PD or death - after 2 or more missing or inadequate post-baseline tumor assessments	Date of last adequate tumor assessment b documenting no PD before new anti-cancer therapy is given or missed tumor assessments	Censored
No PD and no death	Date of last adequate tumor assessment b documenting no PD before new anti-cancer therapy is given or missed tumor assessments	Censored
Treatment discontinuation due to ‘Disease progression’ without documented progression	Not applicable	Information is ignored. Outcome is derived based on documented progression only.
New anti-cancer therapy given	Date of last adequate tumor assessment b documenting no PD before new anti-cancer therapy is given or missed tumor assessments	Censored

a However if the patient dies  $\leq 12$  weeks after the ‘start date’ the death is an event with date on death date

b If there are no adequate post-baseline assessments prior to PD or death, then the time without adequate assessment should be measured from the ‘start date’; if the criteria were met the censoring will be on the ‘start date’.

Kaplan-Meier estimates (product-limit estimates) will be presented by treatment group together with a summary of associated statistics including the median PFS time with 2-sided 95% CIs. In particular, the PFS rate at 3, 6, 9, 12, 15, 18 and 24 months will be estimated with corresponding 2-sided 95% CIs. The CIs for the median will be calculated according to [Brookmeyer and Crowley](#) and the CIs for the survival function estimates at the time points defined above will be derived using the log-log transformation according to [Kalbfleisch and Prentice](#) (conftype=loglog default option in SAS Proc LIFETEST) with back transformation to a CI on the untransformed scale. The estimate of the standard error will be computed using Greenwood’s formula.

Frequency (number and percentage) of patients with each event type (PD or death) and censoring reasons will be presented by treatment group. Reasons for censoring will be summarized according to the categories in Table 5 following the hierarchy shown.

**Table 5. PFS Censoring Reasons and Hierarchy**

Hierarchy	Condition	Censoring Reason
1	No adequate baseline assessment	No adequate baseline assessment
2	Start of new anti-cancer therapy before event.	Start of new anti-cancer therapy
3	Event after 2 or more missing or inadequate post-baseline tumor assessments/ 'start date'	Event after 2 or more missing assessments a
4	No event and [withdrawal of consent date ≥ 'start date' OR End of study (EOS) = Subject refused further follow-up]	Withdrawal of consent
5	No event and lost to follow-up in any disposition page	Lost to follow-up
6	No event and [EOS present OR disposition page for any epoch after screening says patient will not continue into any subsequent phase of the study] and no adequate post-baseline tumor assessment	No adequate post-baseline tumor assessment
7	No event and none of the conditions in the prior hierarchy are met	Ongoing without an event

a 2 or more missing or inadequate post-baseline tumor assessments.

The PFS time or censoring time and the reasons for censoring will also be presented in a patient listing.

### Time of Follow-Up for PFS

A plot will be generated to compare planned and actual relative day of tumor assessments by treatment group. A Kaplan-Meier plot for PFS follow-up duration will also be generated to assess the follow-up time in the treatment groups reversing the PFS censoring and event indicators. Kaplan-Meier estimates (product-limit estimates) will be presented by treatment group together with a summary of associated statistics including the median time of follow-up for PFS with 2-sided 95% CIs. In particular, the rate at 3, 6, 9, 12, 15, 18 and 24 months will be estimated with corresponding 2-sided 95% CIs.

#### 6.2.2.6. Overall survival

Overall survival (OS) is defined as the time from the 'start date' to the date of death due to any cause. Patients last known to be alive will be censored at date of last contact.

$$\text{OS (months)} = [\text{date of death or censoring} - \text{'start date'} + 1] / 30.4375$$

Kaplan-Meier estimates (product-limit estimates) will be presented by treatment group together with a summary of associated statistics including the median OS time with 2-sided 95% CIs. In particular, the OS rate at 3, 6, 9, 12, 15, 18 and 24 months will be estimated with corresponding 2-sided 95% CIs. The CIs for the median will be calculated according to [Brookmeyer and Crowley](#) and the CIs for the survival function estimates at the time points defined above will be derived using the log-log transformation according to [Kalbfleisch and Prentice](#) (conftype=loglog default option in SAS Proc LIFETEST) with back transformation to a CI on the untransformed scale. The estimate of the standard error will be computed using Greenwood's formula.

Frequency (number and percentage) of patients with an event (death) and censoring reasons will be presented by treatment group. Reasons for censoring will be summarized according to the categories in Table 6 following the hierarchy shown.

**Table 6. OS Censoring Reasons and Hierarchy**

Hierarchy	Condition	Censoring Reason
1	No event and [withdrawal of consent date $\geq$ 'start date' OR End of study (EOS) = Subject refused further follow-up]	Withdrawal of consent
2	No event and [lost to follow-up in any disposition page OR data cut-off date – last contact date > 16 weeks]	Lost to follow-up
3	No event and none of the conditions in the prior hierarchy are met	Alive

The OS time or censoring time and the reasons for censoring will also be presented in a patient listing.

### Time of Follow-Up for OS

A Kaplan-Meier plot for OS follow-up duration will also be generated to assess the follow-up time in the treatment groups reversing the OS censoring and event indicators. Kaplan-Meier estimates (product-limit estimates) will be presented by treatment group together with a summary of associated statistics including the median time of follow-up for OS with 2-sided 95% CIs. In particular, the rate at 3, 6, 9, 12, 15, 18 and 24 months will be estimated with corresponding 2-sided 95% CIs.

### 6.2.3. Pharmacokinetic endpoints

#### 6.2.3.1. Pharmacokinetic Analysis of Avelumab and Axitinib

The following pharmacokinetic analyses will be based on the PK analyses set by treatment group.

$C_{\text{trough}}$  and  $C_{\text{max}}$  for avelumab and axitinib will be summarized descriptively (n, mean, SD, CV, median, minimum, maximum, geometric mean, its associated CV, and 95% CI) by treatment group, cycle, and day. Other standard parameters for axitinib will be calculated including, but not limited to  $T_{\text{max}}$ ,  $AUC_{\text{last}}$ ,  $T_{\text{last}}$ ,  $t_{1/2}$ , CL, and  $V_z$ , as data permit. Multiple Dose (MD) -  $T_{\text{ss,max}}$ ,  $AUC_{\text{ss},\tau}$ ,  $t_{1/2}$ ,  $C_{\text{ss,av}}$ , CL, and  $V_{\text{ss}}$ , as data permit.

Dose normalized parameters (eg,  $CDN-C_{\text{max}}$ ,  $CDN-C_{\text{trough}}$ ) will be reported as appropriate. The trough concentrations for avelumab and axitinib will be plotted for each dose using a box whisker plot by cycle and day in order to assess the attainment of steady state.

Pharmacokinetic parameters for avelumab and axitinib will be taken from observed values or derived using non-compartmental methods from plasma concentration-time data as described in Section 3.2.3.

Presentation of pharmacokinetic data will include:

- Descriptive statistics (n, mean, SD, %CV, median, minimum, maximum) of plasma concentrations for axitinib will be presented in tabular form by treatment group, dose level, cycle, day and nominal time. Additionally similar descriptive statistics will also be generated for dose-normalized axitinib pharmacokinetic parameters
- Linear-linear and log-linear plots of mean and median plasma concentrations by nominal time for axitinib will be presented for PK sampling days by cycle and study day. Similar plots will be presented for axitinib for each individual patient concentrations. Only patients who have matched pairs of PK collections available on both planned treatments (when administered alone and in combination with avelumab) will be included in the axitinib plasma concentration descriptive summary and median concentration profiles. Patients who have undergone inpatient dose reduction or escalation will be excluded from the median plasma concentration-time plots.
- Pharmacokinetic parameters for axitinib will be listed and summarized by cycle and study day using descriptive statistics (n, mean, SD, %CV, median, minimum, maximum, geometric mean and its associated %CV, and 95% CI). For Tmax, the range (min, max) will also be provided. Only patients who have a matched pair of estimated axitinib PK parameters available on both planned treatments (when administered alone and in combination) will be included in the axitinib PK parameter summary tables. PK parameters with zero values will be excluded from the calculation of geometric means and its associated %CV. If an inpatient dose escalation or reduction occurs, dose-dependent PK parameters (AUC and Cmax) for that patient may be dose-normalized when it is known that the drug exhibits linear PK within the dose range and other PK parameters will be reported as estimated; or may only be included in descriptive statistics and summary plots up to the time of the dose change. In addition, dose-normalized axitinib Cmax and AUC parameters will be summarized (as described above) using data pooled across cohorts in which different axitinib doses were administered.
- Box plots for AUCτ and Cmax for axitinib (during treatments when given alone and in combination) will be generated. Individual data points, the geometric mean and the median of the parameter in each treatment will be overlaid on the box plots. If a cohort has limited evaluable PK data (n<4), matchstick plots showing changes in AUC and Cmax for each drug (during treatments when given alone and in combination) in individual patients will then be generated. The geometric mean of the parameter in each treatment will be overlaid in the plots. In addition, box plots for dose-normalized axitinib Cmax and AUCτ parameters will be created using data pooled across cohorts in which different axitinib doses were administered.
- Ctrough and Cmax for avelumab will be plotted for each treatment group using a box-whisker plot by cycle and day within cycle in order to assess the attainment of steady-state. Individual data points, the geometric mean and the median of the parameter in each treatment will be overlaid on the box plots.

### **6.2.3.2. Effect of avelumab on axitinib pharmacokinetics**

The effect of repeated avelumab dosing on steady-state axitinib PK will be evaluated using  $C_{max}$  and  $AUC_{\tau}$  of axitinib on Lead-in Day 7 and Cycle 4 Day 1 as the primary PK parameters. The ratio of geometric means of  $C_{max}$  and  $AUC_{\tau}$ , (axitinib in presence of avelumab/axitinib alone) will be computed to assess the magnitude of the effect.

The associated 90% CIs will also be computed for the geometric mean ratios.

### **6.2.4. Population pharmacokinetic endpoints**

Pharmacokinetic and pharmacodynamic data from this study may be analyzed using modeling approaches and may also be pooled with data from other studies to investigate any association between avelumab and axitinib exposure and biomarkers or significant safety/efficacy endpoints. The results of these analyses, if performed, may be reported separately.

### **6.2.5. Biomarker endpoints**

Biomarkers will be summarized at all appropriate timepoints. For soluble proteins this is screening, Lead-in PK D1, C1D1, C2D1, C3D1, C4D1, C6D1, EOT and follow-up at day 30. For Anti-avelumab Antibodies, this is C1D1, C2D1, C3D1, C4D1, C6D1, C8D1, then Q12W, and 30 days after end of avelumab treatment. For biomarkers from Archival FFPE Tumor Tissue Block, this is screening only. For biomarkers from DeNovo Tumor Biopsy, this is screening and end of treatment. Appropriate summary statistics at each timepoint and ratio to screening (for continuous markers) will be provided separately for each dose escalation cohort, the dose expansion cohort, and dose expansion cohort plus the same dose escalation cohort. For continuous biomarkers, ratio to screening within each cohort will be tested using the Wilcoxon Signed-Rank Test when  $n \geq 5$  for a specific timepoint. P-values will be compared to unadjusted and adjusted alpha; alpha will be adjusted using the Bonferroni adjustment (eg,  $0.05/\#$  tests). The adjustment will be determined before data base lock.

To assess whether biomarkers are related to outcome, screening (and ratio to screening for follow-up timepoints, if available) will be summarized versus OR status (0: no OR; 1: OR). For continuous variables, the value of the biomarker will also be displayed in a box plot vs OR status (0: no OR; 1: OR), for each visit.

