In another randomized, open-label, Phase 3 trial, treatment-naïve clear cell RCC patients were randomized (2:1) to receive axitinib (N=192) or sorafenib (N=96). There was no significant difference in median PFS between patients treated with axitinib or sorafenib, 10.1 months (95% CI: 7.2, 12.1) vs 6.5 months (95% CI: 4.7, 8.3) as assessed by Independent Review Committee, respectively, with stratified hazard ratio 0.77 (95% CI: 0.56, 1.05; one sided p=0.038). The axitinib ORR assessed by an Independent Radiology Review Committee was 32%, risk ratio 2.21, (95% CI: 1.31, 3.75, stratified one-sided p=0.0006). Adverse events more common ($\geq 10\%$) with axitinib versus sorafenib were diarrhoea, hypertension, weight decrease, decreased appetite, dysphonia, hypothyroidism, and upper abdominal pain; those more common with sorafenib versus axitinib included palmar-plantar erythrodysesthesia (hand-foot) syndrome and rash, alopecia and erythema.¹³ Toxicities in this clinical trial were generally tolerable and manageable and similar to those observed in clinical trials of axitinib in pre-treated aRCC patients.¹³

Overall, the adverse events reported for axitinib in clinical studies were considered generally tolerable and manageable. For single-agent axitinib, the most common adverse events (>20% of patients) reported from 1445 cancer patients regardless of causality included diarrhea, hypertension, decrease appetite, nausea, weight decreased, dysphonia, palmar-plantar erythrodysesthesia syndrome, hypothyroidism, and proteinuria. Grade ≥ 3 events that occurred most frequently were hypertension, fatigue, and diarrhea.¹¹

Following oral administration, axitinib is rapidly absorbed (median T_{max} 2.5-4.1 hours). The plasma half life of axitinib ranges from 2.5 to 6.1 hours and steady-state is expected within 2 to 3 days of dosing. Dosing of axitinib at 5 mg twice daily resulted in approximately 1.4-fold accumulation compared to administration of a single dose. At steady state, axitinib exhibits approximately linear PK within the 1-mg to 20-mg dose range. The mean absolute bioavailability of axitinib after an oral 5 mg dose is 58%. Axitinib may be administered with or without food. Axitinib is metabolized primarily in the liver by CYP3A4/5 and to a lesser extent by CYP1A2, CYP2C19, and UGT1A1. The predominant sulfoxide and N-glucuronide metabolites in human plasma show approximately ≥ 400 -fold less in vitro potency against VEGFR-2 compared to axitinib.

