3. STUDY DESIGN

3.1. Study Overview

This is a Phase 1b, open-label, multi-center, multiple-dose, safety, PK and pharmacodynamic study of avelumab in combination with axitinib in adult patients with previously untreated aRCC. This clinical study will be composed of a Dose Finding Phase and a Dose Expansion Phase.

The Dose Finding Phase will estimate the MTD and RP2D in patients with aRCC with clear cell histology who did not receive prior systemic therapy for advanced disease, using the modified toxicity probability interval (mTPI) method.²⁹ Dose finding will follow an mTPI design, with up to 3 potential dose levels (DL) to be tested:

- (DL1) avelumab 10 mg/kg Q2W + axitinib 5 mg BID.
- (DL-1A) avelumab 5 mg/kg Q2W + axitinib 5 mg BID.
- (DL-1B) avelumab 10 mg/kg Q2W + axitinib 3 mg BID.

DL-1A and DL-1B will be explored concurrently in a randomized fashion only if the MTD is exceeded in DL1.

To understand the extent of any effects of avelumab on axitinib PK, a 7-day lead-in period with single-agent axitinib will be included prior to Cycle 1 in all patients in the Dose Finding Phase of the study. Since avelumab has a half-life of 3-5 days, it would not be feasible to run a lead-in with avelumab alone to study the PK of avelumab alone. Therefore, the effect of axitinib on avelumab will be evaluated by comparing avelumab trough concentrations at steady state in the presence of axitinib with those reported for avelumab alone in prior studies.

The Dose Finding Phase will lead to the identification of an Expansion Test Dose for avelumab in combination with axitinib in patients with aRCC who did not receive prior systemic therapy for their advanced disease. The Expansion Test Dose will either be the MTD (ie, the highest dose of avelumab and axitinib associated with the occurrence of DLTs in <33% of patients) or the RP2D, ie, the highest tested dose that is declared safe and tolerable by the investigators and sponsor. Once the Expansion Test Dose is identified, the

Dose Expansion Phase will be opened, and avelumab in combination with axitinib will be evaluated in up to approximately 40 patients with previously untreated aRCC.

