## 2.2. Study Design

This is a Phase 1b, open-label, multi-center, multiple-dose, safety, PK and pharmacodynamic study of avelumab in combination with axitinib in adult patients with previously untreated aRCC. This clinical study will be composed of a Dose-finding Phase and a Dose-expansion Phase.

The Dose-finding Phase will estimate the MTD and RP2D in patients with aRCC with clear cell histology who did not receive prior systemic therapy for advanced disease, using the modified toxicity probability interval (mTPI) method. Dose finding will follow an mTPI design, with up to 3 potential dose levels (DL) to be tested:

- (DL1): avelumab 10 mg/kg Q2W + axitinib 5 mg BID
- (DL-1A): avelumab 5 mg/kg Q2W + axitinib 5 mg BID
- (DL-1B): avelumab 10 mg/kg Q2W + axitinib 3 mg BID

DL-1A and DL-1B will be explored concurrently in a randomized fashion only if the MTD is exceeded in DL1.

To understand the extent of any effects of avelumab on axitinib PK, a 7-day lead-in period with single-agent axitinib will be included prior to Cycle 1 in all patients in the Dose-finding Phase of the study. Since avelumab has a half-life of 3-5 days, it would not be feasible to run a lead-in with avelumab alone to study the PK of avelumab alone. Therefore, the effect of axitinib on avelumab will be evaluated by comparing avelumab trough concentrations at steady state in the presence of axitinib with those reported for avelumab alone in prior studies.

The Dose-finding Phase will lead to the identification of an Expansion Test Dose for avelumab in combination with axitinib in patients with aRCC who did not receive prior systemic therapy for their advanced disease. The Expansion Test Dose will either be the MTD (ie, the highest dose of avelumab and axitinib associated with the occurrence of DLTs in <33% of patients) or the RP2D, ie, the highest tested dose that is declared safe and tolerable by the investigators and sponsor. Once the Expansion Test Dose is identified, the Dose-expansion Phase will be opened, and avelumab in combination with axitinib will be evaluated in up to approximately 40 patients with previously untreated aRCC.

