### 3.4. Baseline Variables

#### 3.4.1. Study drug, study treatment and baseline definitions

In this study ‘**study drug**’ refers to avelumab or axitinib and ‘**study treatment**’ (or ‘**treatment group**’) refers to one of the following:

- DL1 with lead-in: axitinib 5 mg oral BID followed by avelumab 10 mg/kg IV Q2W in combination with axitinib 5 mg oral BID, or
- DL-1A with lead-in: axitinib 5 mg oral BID followed by avelumab 5 mg/kg IV Q2W in combination with axitinib 5 mg oral BID, or
- DL-1B with lead-in: axitinib 3 mg oral BID followed by avelumab 10 mg/kg IV Q2W in combination with axitinib 3 mg oral BID, or

- DL1: avelumab 10 mg/kg IV Q2W in combination with axitinib 5 mg oral BID, or
- DL-1A: avelumab 5 mg/kg IV Q2W in combination with axitinib 5 mg oral BID, or
- DL-1B: avelumab 10 mg/kg IV Q2W in combination with axitinib 3 mg oral BID.

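### For soluble proteins, the pooled Cycle 1 Day 1 ratio to screening mixes patients already on axitinib for 7 days with patients not yet treated

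*SAP*

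**What the plan says.** SAP 6.2.5 gives one visit list for both phases of the study: "For soluble proteins this is screening, Lead-in PK D1, C1D1, C2D1, C3D1, C4D1, C6D1, EOT and follow-up at day 30". At each of these visits it asks for summary statistics and, for continuous markers, the ratio to screening. These are wanted for each escalation cohort and for "the dose expansion cohort, and dose expansion cohort plus the same dose escalation cohort". The next sentence adds that "ratio to screening within each cohort will be tested using the Wilcoxon Signed-Rank Test when" at least five values are available at a visit. P-values are compared with an unadjusted alpha and with an adjusted one: "alpha will be adjusted using the Bonferroni adjustment".

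The two cohorts start treatment differently. SAP 2.2 states that "a 7-day lead-in period with single-agent axitinib will be included prior to Cycle 1 in all patients in the Dose-finding Phase", and Protocol 3.1 says the same. SAP 3.4.1 defines the group accordingly: "DL1 with lead-in: axitinib 5 mg oral BID followed by avelumab 10 mg/kg IV Q2W in combination with axitinib 5 mg oral BID". Protocol 5.1 has all other patients begin with the combination. Footnote 1 of the expansion-phase Schedule of Activities places assessments before study treatment unless indicated otherwise.

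SAP 6 records that only DL1 and DL1 with lead-in were used, and that data are shown for each group and for both combined. Nothing in SAP 6.2.5 realigns C1D1 between the groups or leaves it out of the pooled set.

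**The concern.** C1D1 has the same name in both cohorts but describes two different states. Protocol 1.2.2.2 says of axitinib that "steady-state is expected within 2 to 3 days of dosing", so a lead-in patient's C1D1 sample is taken at steady state on one of the two drugs. An expansion patient's C1D1 sample is a second pre-treatment sample. Averaging the two ratios estimates neither the effect of axitinib alone nor the untreated drift since screening.

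A reader of the pooled column would naturally take C1D1 as the visit before combination treatment. If axitinib alone moves a marker, that column could show a change at a visit where most patients are untreated, or dilute a real axitinib effect until it is missed. Which of these happens depends on how many lead-in patients were enrolled.

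**Working it through.** **Inputs from the documents**
- Expansion patients without lead-in: up to about 40 (SAP 5.1.1). The plan's own sizing figure for that number reproduces: 1 − 0.94^40 = 91.6%, which meets the stated 90%. It is not in dispute and only supplies the 40.
- Lead-in patients at DL1: 6 DLT-evaluable patients complete dose finding (SAP 5.1.2). Up to 8 more may be enrolled for axitinib PK (SAP 5.1.1). They follow the dose-finding schedule, lead-in included (SAP 2.2). The range is therefore 6 to 14.

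**Assumptions, not in the documents**
- An axitinib-alone shift of 0.5 in the log ratio, with SD 0.4, normally distributed. Other values are shown below.
- A two-sided test (the SAP does not state sidedness) at unadjusted 0.05.
- Expected log ratio of zero at an untreated C1D1.

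**Step 1: share of lead-in patients in the pooled set**
- 6/(6 + 40) = 6/46 = 13%
- 14/(14 + 40) = 14/54 = 26%

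**Step 2: expected pooled log ratio = shift × share**
- 0.5 × 6/46 = 0.07
- 0.5 × 14/54 = 0.13

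The lead-in group alone would show 0.5 and the expansion group 0.

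**Step 3: rejection by the Wilcoxon signed-rank test on simulated log ratios (shift 0.5, SD 0.4)**

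| Lead-in patients | Pooled | Lead-in alone | Expansion alone |
|---|---|---|---|
| 6 | about 12–14% | about 51–54% | about 5% |
| 14 | about 48% | about 98–99% | about 5% |

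Ranges are the spread between repeat simulations.

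**Step 4: sensitivity to the assumptions**
- 14 lead-in patients, shift 0.2, SD 0.4: pooled rejection about 15%.
- 14 lead-in patients, shift 0.5, SD 0.6: about 27%.
- Doubling of the marker (log shift 0.69): 23% (SD 0.3) or 12% (SD 0.6) with 6 lead-in patients; 84% or 45% with 14.
- Bonferroni with an assumed 20 tests, shift 0.5, SD 0.4: about 1% with 6 lead-in patients and 9% with 14.
- No axitinib effect: about 4–6%, the nominal level.

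With the biology held fixed, the pooled result changes several-fold with the number of lead-in patients alone.

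**The case against.** The best defence is that the unmixed results are already planned. SAP 6.2.5 and SAP 6 both call for the escalation and expansion groups to be shown separately. A reader might infer that pooling by visit name destroys the information the lead-in provides. It does not: the lead-in C1D1 ratio and the expansion C1D1 ratio each appear in their own column. This stands, and it limits the point to the pooled column.

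Four further limits also stand.
- **Soluble proteins only.** Tumour-tissue markers are sampled at screening, or at screening and end of treatment, so they have no C1D1 value. The unredacted secondary biomarker endpoint is tumour-tissue status. It would be wrong to say that the biomarker analysis as a whole is affected.
- **The test is a reading.** Testing is specified within each cohort. The natural reading covers all three groupings named in the sentence before. On a narrower reading the combined set is summarised but not tested. The mixed summary remains either way.
- **Pre-dose sampling is inferred.** The blood-biomarker row and footnote of the expansion schedule are redacted, so the untreated state at C1D1 rests on the general rule.
- **Fourteen lead-in patients is the maximum.** The 8 PK patients are optional, and the documents do not say whether they count in the escalation cohort. The 48% figure should not be quoted without the 12–14% beside it.

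A reader might also infer that a pooled C1D1-to-C2D1 change is confounded. No such comparison is planned: every change is a ratio to screening, which is untreated in both groups.

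What the defence does not supply is a meaning for the pooled C1D1 ratio when axitinib alone moves the marker.

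**Conclusion.** The concern holds for one timepoint in one column: the pooled soluble-protein ratio to screening at C1D1 and, on the natural reading, its test. As written, that value combines an axitinib-alone state with an untreated state in proportions fixed by enrolment. The pooled mean carries 13% to 26% of any axitinib-alone effect. Under the assumed shift of 0.5 log units and SD 0.4, unadjusted rejection runs from about 12–14% to 48%.

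This rests on pre-dose C1D1 sampling in the expansion phase and on axitinib alone changing the marker; the documents give no size for that change. The study plans no formal hypothesis testing (SAP 5.1.1), so the consequence is an uninterpretable exploratory entry and not a wrong trial conclusion. It is still worth correcting, because the correction is a matter of wording.

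**What to change.** Amend SAP 6.2.5 for soluble proteins as follows.
1. Report and test C1D1 by lead-in status only, labelled *axitinib alone, after 7 days* for lead-in patients and *pre-treatment* for expansion patients. Defining the split by lead-in status also covers any additional PK patients, whichever cohort they are assigned to.
2. Restrict the pooled expansion-plus-escalation summary and test to C2D1 onward. Add a note that lead-in patients have had 7 more days of axitinib at each of those visits.
3. Keep screening as the denominator throughout. Changing it to the last pre-drug sample would redefine every later ratio, and this problem does not require that.
4. State whether the combined set counts as a cohort for the signed-rank test, so that the Bonferroni count is fixed before database lock.

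Optionally, add C2D1/C1D1 in lead-in patients as a descriptive summary of the change after avelumab is added.

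The cost is SAP wording and one fewer pooled timepoint. No new samples are needed, and the number of tests does not rise.
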